1.2 SCHEDULE OF ACTIVITIES (SOA)

Procedures	Phase 0							Expansion				Safety Phone Call ~30 days after last dose	Survival Follow Up Phone Call / Letter
	Screening Day -28 to -1	Enrollment/Baseline Day 1	Days 2-5	Pre-surgical Assess. Day 6	Surgical Visit Day 7	Post-op Follow Up ~7 days after last dose	Cycle 1 (28 days) 	Cycle 2 (28 days) 	Subsequent Cycles (28 days) 	End of Study Treatment			
Visit #	1	2	n/a	3	4	5	6-8	9-11	12, 13...	Last	n/a	n/a	
Informed consent	X												
Collect archival/biopsy tissue	X												
Demographics	X												
Medical history	X												
Diagnosis and extent of cancer	X												
Eligibility	X	Pre											
Concomitant medication review	X			X-----X									
Adverse event review and evaluation	X			X-----X							X		
Surgical and medical procedures	X			X-----X									
Phone Call / Letter											Phone	~Q3 months 	
TREATMENT/DRUG ADMINISTRATION													
Administer study drug		QD	QD (Home)	QD	QD		X 	X 	X 				
Review of Home Dosing Diary		X		X	X		1	1	1	X			
Drug Compliance / Accountability		X		X	X		1	1	1	X			
CLINICAL PROCEDURES													
Physical exam	X 										X		
Neurological exam	X 										X		
Brief Physical and Neurological exam						X	1	1	1				
Ophthalmologic Evaluation 	X 					X			C3D1 and every 4 months after	X			
ECOG	X	X				X	1	1	1				
Vital signs	X 			X		X	1	1	1	X			

A Phase 0 Study of Infigratinib in Recurrent Glioblastoma Patients

Protocol 2020-08

	Phase 0								Expansion			Survival Follow Up Phone Call / Letter
	Screening Day -28 to -1	Enrollment/Baseline Day 1	Days 2-5	Pre-surgical Assess. Day 6	Surgical Visit Day 7	Post-op Follow Up ~ 7 days after last dose	Cycle 1 (28 days) 	Cycle 2 (28 days) 	Subsequent Cycles (28 days) 	End of Study Treatment		
Procedures												
Height	X 											
Weight	X 									X		
12-Lead ECG 	X	X		X			1	1	1	X		
Craniotomy					X							
LAB PROCEDURES												
Hematology (CBC w/diff) 	X 						X	1	1	1	X	
Serum chemistry 	X 						X	1	1	1	X	
Pregnancy test 	X 						X	1	1	1	X	
Coagulation 	X 											
Urinalysis 	X 						X	1	1	1	X	

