Pharmacokinetic (PK) blood sample		Pre			X 		1, 8, 15	1, 8, 15				
Pharmacokinetic (PK) CSF sample					X 							
Pharmacokinetic (PK) tumor sample					X 							
Pharmacodynamic (PD) blood sample		Pre										
Pharmacodynamic (PD) tumor sample	Archival/ biopsy				X 							
Pharmacogenomic (PG) tumor tissue	Archival/ biopsy											
Patient Derived Xenograft (PDX) tumor sample					X 							
IMAGING PROCEDURES												
MRI – Brain with/without contrast	X 					X 	MRI Q3 months 		Last			
RANO						X	Q3 months		Last			
ADMINISTRATIVE PROCEDURES												
Complete Case Report Forms (CRFs)	X	X		X	X	X	X	X	X	X	X	X
1. Expansion Cohort: study drug administration is every day (QD) 3 weeks on/ 1 week off 2. Screening assessment may be completed at D1 pre-dose, if completed at screening, does not need to be repeated at D1 pre-dose except for ECG and ECOG. Results must be available to confirm eligibility prior to dosing.												

A Phase 0 Study of Infigratinib in Recurrent Glioblastoma Patients

Protocol 2020-08

Procedures	Phase 0						Expansion				Safety Phone Call ~30 days after last dose	Survival Follow Up Phone Call / Letter
	Screening Day -28 to -1	Enrollment/Baseline Day 1	Days 2-5	Pre-surgical Assess. Day 6	Surgical Visit Day 7	Post-op Follow Up ~7 days after last dose	Cycle 1 (28 days) 	Cycle 2 (28 days) 	Subsequent Cycles (28 days) 	End of Study Treatment		

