
3. Single ECG. At Screening: If the QTcF is >470 msec in the first ECG, a total of 3 ECGs separated by at least 5 minutes should be performed. If the average of these 3 consecutive results for QTcF is ≤470 msec, the participant meets eligibility in this regard.
 
4. See Section 8.2.12.
 
5. Serum pregnancy test (women of childbearing potential) at screening. Urine pregnancy test (women of childbearing potential) at remaining visits pre-dose (if applicable).
 
6. PK blood samples will be obtained on D1 pre-dose and on D7 at pre-dose (trough level), 0.5, 1, 2, 4, 6, 8, 24 (trough) hours post dose (<math>\pm</math>5 min window for 0.5hr and 1hr; <math>\pm</math>15min window for 2, 4, 6hr; <math>\pm</math>1hr for 8 and 24 hours post dose).
 
7. PK CSF, Tumor and blood samples will be collected intra-operatively at approximately 8 hours post-dose (<math>\pm</math>1 hour)
 
8. PD/PDX Tumor sample will be collected intra-operatively at approximately 8 hours post-dose (<math>\pm</math>1 hour)
 
9. MRI completed as Routine Care. At screening, utilize the most recent MRI available. At follow-up, utilize the first MRI obtained post-operatively.
 
10. The start of follow up for long-term survival begins following completion of the Day 30 safety follow up call.
 
11. Ophthalmic exam should include visual acuity testing (including corrected distance acuity), slit lamp examination of the anterior eye segment, intraocular pressure (IOP), retinal OCT and dilated fundoscopy. Additional examinations such as specular microscopy and corneal pachymetry will be performed as clinically indicated. In addition, ophthalmic exams should be done as clinically indicated.
 
12. A visit window of <math>\pm</math>1 day in Cycle 1 and 2 on Days 1, 8, and 15 and <math>\pm</math>3 days in Cycle 3 onward is allowed.
												

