#### 5.3.1 GENERAL GUIDANCE FOR WOMEN OF CHILDBEARING POTENTIAL AND/OR USE OF CONTRACEPTIVE METHODS

Infigratinib could cause fetal harm and developmental abnormalities. Advise participants of the potential risk to the fetus and to use effective contraception while on infigratinib and for at least 3 months following the last dose. ([QED 2019](#))

- A female of childbearing potential must have a negative serum pregnancy test within 28 days of the first dose of infigratinib and agree to use a highly effective contraception method for at least 1 month prior to treatment and for 3 months following the last dose of infigratinib.
- Contraceptive methods may include an intrauterine device [IUD] or barrier method. If condoms are used as a barrier method, a spermicidal agent should be added as a double barrier protection.
- Use of condoms or other methods to ensure effective contraception with partner and for an additional 3 months after the end of treatment administration. A condom is required to be used also by vasectomized men as well as during intercourse with a male partner to prevent delivery of the drug via seminal fluid.
- Cases of pregnancy that occur during maternal exposures to infigratinib should be reported. If a patient or spouse/partner is determined to be pregnant following infigratinib initiation, she must discontinue treatment immediately. Data on fetal outcome and breast-feeding are to be collected for regulatory reporting and drug safety evaluation.

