### 8.3.9 REPORTING OF PREGNANCY

Pregnancy is not considered an adverse event unless it is a spontaneous abortion. Each pregnancy occurring while the participant is on study treatment must be reported to IBTC-CC within 24 hours of learning of its occurrence. Participants who become pregnant during the trial must be withdrawn. The pregnancy will be followed up from the estimated date of delivery plus 3 months to determine outcome, including spontaneous or voluntary termination, details of the birth, and the presence or absence of any birth defects, congenital abnormalities, or maternal and/or newborn complications.

Women of childbearing potential should be advised to use highly effective contraception methods while they are receiving study treatment and up to 3 months after treatment has been stopped.

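### A woman's first infigratinib dose may rest on a pregnancy test up to 28 days old with no required Day 1 repeat, and footnote 5 leaves urine testing in Phase 0 unclear

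*Combined protocol and SAP*

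**What the plan says.** Section 5.3.1 states that a female of childbearing potential "must have a negative serum pregnancy test within 28 days of the first dose of infigratinib". Inclusion criterion 13 asks for a negative serum test before treatment starts and sets no shorter limit. The screening column of the Schedule of Activities (SoA) is headed "Screening Day -28 to -1".

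The SoA pregnancy row is marked at screening, with footnote 2 attached, and is empty for Day 1, Days 2-5, Day 6 and Day 7. The next marks are the post-operative visit, Day 1 of each Expansion cycle, and end of treatment. The laboratory rows appear shifted by one column in the extracted text, but neither alignment puts a mark on Days 1 to 7.

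Footnote 2 lets a screening assessment be done on Day 1 before dosing. If it was done earlier, the rule is "if completed at screening, does not need to be repeated at D1 pre-dose except for ECG and ECOG". It adds: "Results must be available to confirm eligibility prior to dosing".

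Footnote 5, on the pregnancy row itself, asks for serum at screening and then: "Urine pregnancy test (women of childbearing potential) at remaining visits pre-dose (if applicable" (the parenthesis closes there). Table 9 in Section 8.2.12 gives a serum test at screening and a urine test at subsequent cycles.

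On the hazard, Section 5.3.1 says: "Infigratinib could cause fetal harm and developmental abnormalities". If a pregnancy is found, "she must discontinue treatment immediately" (5.3.1), and Section 8.3.9 adds: "Participants who become pregnant during the trial must be withdrawn".

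**The concern.** Phase 0 contains the participant's first exposure to a drug that the plan treats as a possible fetal hazard. It is also the only dosing block whose start has no test of its own marked in the grid. Eligibility is rechecked before the Day 1 dose, but the pregnancy criterion may be confirmed from a result four weeks old. A pregnancy that began after that test would pass the check unseen. The plan's own response to a pregnancy is to stop the drug and withdraw the participant, so the purpose of testing is best served just before the first dose.

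Footnote 5 adds a practical difficulty. A site may take the remaining visits to mean only those marked in the row. It may also take them to mean every later visit at which a dose is given, which would include Days 1 and 7, and Day 6 when that dose is taken in clinic. Up to three sites will enrol, and nothing in the text tells them which to follow.

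**Working it through.** This is day counting; no statistical model is involved.

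**Inputs**
- Screening runs from Day -28 to Day -1 and dosing starts on Day 1, so there is no Day 0 (SoA).
- Phase 0 doses are given on Days 1 to 7. Days 1 and 7 are in clinic, and Day 6 is at home or in clinic (Section 6.1.2, Table 2).
- The limit on the serum test is 28 days before the first dose (5.3.1).
- Expansion tests fall on Day 1 of each cycle (SoA), and Expansion doses on Days 1 to 21 (6.1.2).
- The sample is 20 participants (Section 9.1). The number of women of childbearing potential is not given.

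**1. Reproduce the plan's figure.** From Day -28 to Day 1 with no Day 0: 1 - (-28) - 1 = 28 days. This equals the limit in 5.3.1. If a Day 0 existed the count would be 29, but 5.3.1 would still cap it at 28.

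**2. Carry it to the last Phase 0 dose.** Dose 7 falls 7 - 1 = 6 days after dose 1, so the maximum is 28 + 6 = 34 days.

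**3. Range over permitted test dates**

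| Serum test done on | Age at dose 1 | Age at dose 7 |
|---|---|---|
| Day -28 | 28 days | 34 days |
| Day -1 | 1 day | 7 days |
| Day 1 pre-dose (footnote 2 option) | 0 days | 6 days |

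**4. What footnote 5 would add**
- Marked visits only: 0 urine tests on Days 1 to 7, and the table above applies.
- Every later dosing visit: tests on Days 1 and 7, so 2, or 3 if the Day 6 dose is taken in clinic. The test is then 0 days old at dose 1 and at dose 7.

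**5. Comparison with Expansion.** From the Day 1 test to the Day 21 dose: 21 - 1 = 20 days. At nominal visit dates the test is 0 to 20 days old at any dose, and 0 days at the first dose of each cycle.

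**6. After the fix.** With a test on Day 1 before dosing, the age is 0 days at dose 1 and 7 - 1 = 6 days at dose 7.

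**7. Volume of testing.** Assume that 10% to 30% of participants are women of childbearing potential: 0.10 x 20 = 2 to 0.30 x 20 = 6 women. At one urine test each, the fix means at most 2 to 6 tests in Phase 0. The wide reading of footnote 5 would mean 2 x 2 = 4 to 6 x 3 = 18.

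**The case against.** A reader might infer that the passages contradict one another. They need not. Footnote 5 is attached to the pregnancy row and carries an if-applicable qualifier. Read as covering the visits marked in that row, it agrees with the grid, footnote 2, Table 9 and 5.3.1. The wide reading also fits the rest of the grid poorly: it would call for tests on Days 8 and 15 of Cycles 1 and 2, where the row shows Day 1 only. What stands is an ambiguity of wording.

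A reader might also infer that the age of the test is left open. It is not: 5.3.1 sets 28 days, and the screening window matches. A shorter limit would be a change to a stated rule. Nor does footnote 2 rule out a test on Day 1, since it allows the screening test itself then and waives only a repeat.

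Two safeguards deserve credit. Inclusion criterion 14 requires highly effective contraception from at least one month before screening, so the remaining route is contraceptive failure or non-use. The post-operative visit, about seven days after the last Phase 0 dose, appears to carry a test before any Expansion dosing.

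All of this stands, and it lowers the probability and the weight of the point. None of it requires a Day 1 test for a woman screened on Day -28, and the post-operative test comes after all seven doses.

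**Conclusion.** The plan's stated rules allow first exposure to infigratinib on a serum test up to 28 days old, and dose 7 on one up to 34 days old, with no repeat required in between. These are maxima; a site that uses the footnote 2 option has 0 and 6 days. Footnote 5 is ambiguous about Days 1, 6 and 7 and should be settled.

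This is a cheap safety improvement. The documents do not support any statement about how often a pregnancy would be missed. The event is unlikely in any one woman, and the number of women concerned (2 to 6) rests on an assumed share of 10% to 30%. The case for acting is that the consequence is serious by the plan's own account, each Expansion cycle already starts with a test, and the remedy fits into an existing pre-dose eligibility check.

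**What to change.** - In the SoA, mark a urine pregnancy test at Day 1 pre-dose for women of childbearing potential, unless the screening serum test is done that day.
- In footnote 2, add this urine test to the exception that now names ECG and ECOG.
- Reword footnote 5 to: serum at screening; urine at Day 1 pre-dose (unless serum is done that day) and at each later visit marked in the grid. Give Table 9 the same wording in place of its reference to subsequent cycles.

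The cost is a wording amendment and at most one urine test per woman concerned. The Day 1 visit is already in clinic, with a pre-dose ECG, ECOG assessment, blood samples and eligibility check.

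There is one downside. A site that now follows the wide reading of footnote 5 would no longer be required to test on Days 6 and 7. It would go from 2 or 3 Phase 0 urine tests to 1, and its test age at dose 7 would rise from 0 to 6 days. If the sponsor prefers the wide reading, marking Days 1, 6 (when dosed in clinic) and 7 would also remove the ambiguity, at 2 or 3 tests per woman.

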## 2 INTRODUCTION

### 2.1 STUDY RATIONALE

#### 2.1.1 RATIONALE AND PURPOSE

Primary brain tumors are among the top 10 causes of cancer-related deaths in the United States, accounting for approximately 1.4% of all cancers and 2.4% of all cancer-related deaths. About 14 per 100,000 people in the United States are diagnosed with a primary brain tumor each year, and 6 to 8 per 100,000 are diagnosed with a WHO grade III or IV primary brain tumor. Glioblastoma multiforme (GBM, WHO Grade IV gliomas) is the most frequently reported malignant brain tumor histology (29.6%) in the National Cancer Database. The prognosis for patients who develop WHO Grade III or IV gliomas is bleak, with average survival after diagnosis ranging from 12-16 months. Although conventional treatment with surgery, irradiation, and temozolamide postpones tumor progression and extends patients survival, these tumors universally recur and unrelentingly result in patient death. Therefore, new targeted agents are urgently needed for high-grade glioma patients.

Phase 0 trials identify promising new drugs by ‘humanizing’ preclinical studies. An array of design variations exists under the Phase 0 umbrella to address a range of possible study objectives. These include studies to (1) determine whether a mechanism of action (MOA) defined in nonclinical models is achievable in humans; (2) refine a biomarker assay using human tumor tissue; (3) develop a novel imaging probe and evaluate its distribution, binding characteristics, and target effects in humans; (4) evaluate the human pharmacodynamics (PD) and/or pharmacokinetics (PK) of 2 or more analogs to select the most promising candidate for further development; (5) determine a dose-range and sequence of administration of a biomodulator for use in combination with established chemotherapy; and (6) provide human PK-PD relationship data for an agent before Phase 1 testing. For CNS oncology studies, PK analysis refers to measurement of study drug concentration in brain tumor tissue and PD analysis refers to quantification of a molecular/cellular target influenced by the study drug.

For brain tumor patients, Phase 0 clinical trials are challenging, not only due to trial logistics, but also because of the dampening effect the non-therapeutic nature of such studies has on patient accrual. A Phase 0 + Expansion trial adapts the Phase 0 strategy to brain tumor patients but incorporates a PK- and PD-dependent trigger that graduates Phase 0 patients into an exploratory Expansion study arm. In doing so, this tactic is compelling to potential brain tumor patients by providing them with the confidence that, if selected for treatment, there is biological evidence suggesting their tumor can respond. For these patients graduating to the Expansion Arm, they (and their providers) are motivated by the biological rationale connecting the experimental therapy to their individual cases. Anecdotally, our institutional experience with both Phase 0 and Phase 0 + Expansion Arm studies speaks to this advantage and, since transitioning to the latter model in 2016, patient accrual has increased from 14% to 35%. While the Phase 2 component is typically exploratory, it can be randomized, as well.

Less than 1% of all published clinical trials for brain tumors contain both PK and PD endpoints evaluating tissue effects following initial drug exposure. Fewer studies, however, examine tissue from these same patients following extended periods of drug treatment, even though 19% of all high-grade glioma patients, for example, undergo 3 or more tumor resections. Using the Phase 0/2 study paradigm, patients with planned re-resections for tumor recurrence following therapeutic dosing of the experimental agent(s) provide a critical opportunity for longitudinal tissue analysis. Within this population, enhancing and nonenhancing tumor tissue from fast- vs. slow-recurring tumors can be compared to identify the roles of

## A Phase 0 Study of Infigratinib in Recurrent Glioblastoma Patients Protocol 2020-08

on-target and off-target pathways in tumor escape. To control for interindividual variations in CNS drug penetration, putative resistance mechanisms can also be examined in matched tissue specimens from initial, second (Phase 0), and third (Expansion Arm) resections. Beyond characterizing resistance mechanisms, planned identification of tissue biomarker signatures associated with susceptibility to experimental agents can inform future clinical trial designs. For patients completing the Phase 0 component of the study with evidence of adequate tumor penetration (i.e., a ‘positive’ PK endpoint), variations in observed PD effects provide an opportunity to distinguish biological responders (i.e., patients with positive PK and PD endpoints) from non-responders (i.e., patients with a positive PK endpoint and negative PD endpoints). Using a variety of molecular and genetic techniques, a menu of tumor biomarker combinations predictive of pharmacodynamic sensitivity to the study drug(s) can be formulated for prospective interrogation. Taken together, these longitudinal studies of human brain tumors exposed to experimental therapies can provide actionable evidence for future strategies.

Thus, the Phase 0 clinical trial mechanism originally proposed by the FDA was conceived with the general drug development community in mind. Brain tumor drug development, however, poses unique study limitations due to the absence of predictive animal models, the significant risks of tumor acquisition, the unsuitability of microdosing, the challenge of the BBB, and the potentially confounding effects of neurosurgical anesthesia. Adapting the Phase 0 trial paradigm for neuro-oncology patients is an effective avenue to obtain direct evidence of drug delivery and target modulation. Specific modifications included in this proposal are: (1) abandoning microdosing in favor of a higher-dose regimen, (2) using archival or biopsy tissue as a pretreatment control specimen, (3) incorporating CSF into PK and PD analyses, and (4) adding a Phase 2 component for patients with demonstrable PK and PD responses.

Chromosomal translocations that fuse in-frame members of the FGFR (fibroblast growth factor receptor) and TACC (transforming acidic coiled-coil containing proteins) gene families (the FGFR-TACC gene fusions) were first described in 2012 in human GBMs ([Singh, et al. 2012](#)) and later in several other cancer types. The finding that a subset of GBMs harbor oncogenic fusions of FGFR-TACC has raised hope that inhibition of FGFR with FGFR kinase inhibitors could be a valuable therapeutic option for this subgroup of deadly brain cancer ([Lasorella, et al. 2017](#)). From epidemiological estimates based on published literature and other publicly available sources such as cBioPortal datasets, FGFR3-TACC3 rearrangements were present in 2.4% of GBM. In addition, gain-of-function mutations in FGFR1 and FGFR3 were present around 0.5% of GBM cases. Together, there are ~ 3-4 % of GBMs suitable for FGFR kinase inhibitor treatment.

Infigratinib phosphate (formerly BGJ398, also known as BBP-831, hereafter referred to as infigratinib) is an orally bioavailable, potent, selective ATP-competitive inhibitor of fibroblast growth factor receptor (FGFR) 1-3. [REDACTED]

[REDACTED] . ([QED 2019](#))

## 2.2 BACKGROUND

### 2.2.1 INFIGRATINIB NONCLINICAL STUDIES

See the infigratinib IB for additional nonclinical information ([QED 2019](#))

### 2.2.2 INFIGRATINIB CLINICAL STUDIES

See the infigratinib IB for additional clinical information ([QED 2019](#))

## 2.3 RISK/BENEFIT ASSESSMENT

### 2.3.1 KNOWN POTENTIAL RISKS

#### 2.3.1.1 INFIGRATINIB

More information about the known and expected risks, serious adverse events (SAEs) and reasonably anticipated AEs of infigratinib are found in the IB ([QED 2019](#)).

### 2.3.2 KNOWN POTENTIAL BENEFITS

More information about the known and expected benefits of infigratinib are found in the IB ([QED 2019](#)).

### 2.3.3 ASSESSMENT OF POTENTIAL RISKS AND BENEFITS

The preliminary efficacy signals observed in oncology clinical trials, combined with the emerging safety profile of infigratinib, warrant continued development of this compound for the treatment of solid tumors with genetic alterations of the FGFR pathway.

[REDACTED]  
(QED 2019).

